7.5 Long Term Intervention Period

During Visit 3 patients will be asked whether they want to:

a) continue with their already assigned treatment;

Patients will continue with their respective rehabilitation programs.

b) switch to the other arm;

If patients on the conventional physiotherapy arm would like to start the FeetMe program they will be trained to use the devices and will start their 12 weeks program. Patients of FeetMe group wanting to switch from FeetMe to CPt will need to arrange the care themselves. Patients who switch will have the same visit schedule as during the first three months.

c) discontinue rehabilitation.

If a patient would like to discontinue rehabilitation they will still be asked to remain in the study for further data collection.

7.5.1 Remote Gait Monitoring 2

At the end of Visit 3, all patients will perform a second remote gait monitoring period. All patients will use the insoles remotely while performing their day-to-day activities (including physiotherapy) for 2 weeks. Data will be recorded in standalone mode (without a phone).

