	Change from baseline to Week 12 (Visit 3) in Stance Time Variability assessed during the 6MWT.
	Secondary Endpoints
	• Rate of falls at Week 12 based on the results of the falls diary.
	• Change from baseline to Week 12 (Visit 3) in the asymmetry of the swing duration assessed during the 6MWT.
	• Change from baseline to Week 12 (Visit 3) in the Mini-BESTest.
	• Change from baseline to Week 12 (Visit 3) in Unified Parkinson's Disease Rating Scale (MDS-UPDRS) Part III sub-score.
	• Change from baseline to Week 12 (Visit 3) in the results of the Parkinson Disease Questionnaire (PDQ-39).
	Exploratory Endpoints
	• Rate of falls at Week 24 based on the results of the falls diary.
	• Change from Baseline to Week 24 (Visit 4) and from Week 12 (Visit 3) to Week 24 in:
	- Gait velocity (cm/s) assessed during the 6MWT
	- Stance Time Variability assessed during the 6MWT
	- Asymmetry of the swing duration assessed during 6MWT
	- the Mini-BESTest
	- MDS-UPDRS Part III sub-score
	- the results of the PDQ-39
	 Change from Baseline to Week 12 (Visit 3) and to Week 24 (Visit 4) and from Week 12 to Week 24 in the:
	- gait parameters measured by the FeetMe Monitor during the 6MWTs other than ones of the primary and secondary endpoints
	- gait parameters measured by the FeetMe Monitor during remote gait monitoring
	- results of the pain VAS
	- results of the Parkinson Disease Sleep Scale 2 (PDSS2)
	- results of the Clinical and Patient Global Impression of Severity scales (CGI/PGI-S)
	- results of the Clinical and Patient Global Impression of Improvement scales (CGI/PGI-I)
	• results of the MDS-UPDRS I, II and IV sub scores
	• Actual versus prescribed time spent on physiotherapy at Week 12 and Week 24.
· · · · · · · · · · · · · · · · · · ·	

	• Results of the Patient and Investigator satisfaction questionnaire.
	• Number of device and protocol procedure related adverse events at Week 12 and at Week 24.

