6.2 Schedule of Assessments

Table 6.1 Schedule of Assessments

CIP Number 2023-A00150-45 Final version 0.2

CONFIDENTIAL May 2023

			Primary Inter	vention Period		Long Term Intervention Period			
Visit	Screening ¹	Baseline ²	Visit 1	Visit 2	Visit 3	Visit 1.2	Visit 2.2	Visit 4	End of Study Visit
Timepoint	Day 1	Day 1	Week 4	Week 8	Week 12	Week 16	Week 20	Week 24	Week 26
Visit Window	NA	NA	\pm 7 days	\pm 7 days	\pm 7 days	\pm 7 days	\pm 7 days	\pm 7 days	\pm 7 days
Assessments	In-Clinic + Remote	In-Clinic	Remote	Remote	In-Clinic	Remote	Remote	In-Clinic	Remote
						patients	who switch		
ICF	•								
Eligibility Check	•								
Modified Hoehn and Yahr staging	•							•	
MoCA	•								
Medical History & Demographics		•							
Randomisation	•								
Prior Rehabilitation History	•								
Prior- and Concomitant Medication	•			-	•				
6MWT ³		•			•			•	
Ecological remote gait data collection		for 2 weeks after BL			for 2 weeks after V3			for 2 weeks after V4	
Mini-BESTest		•			•			•	
MDS-UPDRS		•			•			•	

CIP Number 2023-A00150-45 Final version 0.2

CONFIDENTIAL May 2023

FOG-Q	•			•			•	
PDSS-2	•	•	•	•	•	•	•	
Pain VAS	•	•	•	•	•	•	•	
PDQ-39	•			•			•	
PDQ-8		•	•		•	•		
CGI-S / PGI-S	•							
CGI-I / PGI-I				•			•	
Satisfaction Questionnaire	•			•			•	
Falls diary								
Conventional Physiotherapy tracking		From ICF to EOS						
AEs								
Adherence				•			•	

ICF: Informed Consent Form; 6MWT: 6 Minutes Walk Test; Mini-BESTest: Mini Balance Evaluation Systems Test; MOCA: Montreal Cognitive Assessment; AEs: Adverse Events; FOG-Q: Freezing of Gait Questionnaire; MDS-UPDRS I, II & III: Unified Parkinson's Disease Rating Scale parts I, II and III; PDQ-39: Parkinson Disease Questionnaire; PDQ-8: Parkinson Disease Questionnaire Short Form; CGI-S/PGI-S: Clinical/Patient Global Impression of Severity; CGI-I/PGI-I: Clinical/Patient Global Impression of Improvement; PDSS-2: Parkinson Disease Sleep Scale 2;

¹A reflection period of fifteen to thirty days must be given to the subject to decide upon their participation.

² BL assessments will take place right after the Screening Visit.

³ Patients on the FeetMe arm will perform weekly 6MWTs as part of their rehabilitation program using the FeetMe Rehabilitation application.

Note: Visit windows are to be calculated compared to the original schedule, not the previous visit

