7.4 Primary Intervention Period

Following the Baseline Visit, all patients will begin their 12-week physiotherapy (or no-physiotherapy) regimen according to their randomisation.

During this period:

- All patients will participate in the Remote Gait Monitoring 1 and Visits 1-3 (Sections 7.3.1, 7.3.2, 7.3.3).
- Patients on the Conventional Physiotherapy arm, if they have access to it will start or continue their conventional physiotherapy and will keep track of it using the Conventional Physiotherapy Tracking Sheet (Appendix F). Patients who did not have access to CPt at the time of inclusion but manage to arrange one during the Primary Intervention Period will restart their PIP.
- On the other arm patients will start the FeetMe rehabilitation program (Section 4.4, Appendix A and B).
- In addition, all patients will keep a falls diary (Appendix G).

7.4.1 Remote Gait Monitoring 1

At the end of the Baseline Visit, all patients will take the FeetMe Insoles, mobile devices and chargers with them to their homes. A Patient User Guide will be provided.

- All patients will use the insoles remotely while performing their day-to-day activities (including physiotherapy) for two weeks. Data will be recorded in standalone mode (without a phone).
- Patients will download the data from the insoles at the end of each day.

7.4.2 Visits 1 and 2

Four and eight weeks after Baseline Visit, two remote visits (Visit 1 and 2) will take place. Patients will be asked to fill in the following questionnaires:

- PDSS-2
- Pain VAS
- Parkinson Disease Questionnaire, Short Form (PDQ-8).

7.4.3 Visit 3

Twelve weeks after Baseline Visit, that is, at the end of the 12-week Primary Intervention Period, all patients will participate in an in-clinic visit (Visit 3), where they will perform the same series of assessments as in the Baseline Visit. Patients will need to bring their FeetMe devices, their diaries, trackers and filled-in questionnaires to the visit.

The following assessments will be performed at Visit 3:

- Gait Assessments, which must be performed in the ON-phase:
 - 6 Minutes Walk Tests (6MWT)
 - Mini-BESTest.

During the 6MWT and the Mini-BESTest patients must wear the insoles. Specific instructions set out in the Site User Manual must be followed when setting up and executing the assessments.

- Disease specific rating scales:
 - MDS-UPDRS
- Other Assessments:
 - FOG-Q
 - PDSS2
 - Pain VAS
 - PDQ39

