 - Clinical Global Impression of Improvement / Patient Global Impression of Improvement (CGI/PGI-I)
- Potential adverse events and change in concomitant medication since the last contact.
- The source documents must be collected from the patients and the diary and tracker transcribed into the database.
- Also, the patients further allocation is to be decided (Section 7.4).
- At the end of the visit the patients will return home with their devices (as applicable based on their new or unchanged treatment) and proceed into the Remote Gait Monitoring 2 (Section 7.4.1).

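### Remote gait has no recording from the end of the randomised period: its Week 12 value is collected in weeks 12–14, after patients may have switched or stopped

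*Protocol*

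**What the plan says.** The Synopsis (Exploratory Endpoints), repeated in Table 5.1, sets the time points as "Change from Baseline to Week 12 (Visit 3) and to Week 24 (Visit 4) and from Week 12 to Week 24 in the" and includes among the variables "gait parameters measured by the FeetMe Monitor during remote gait monitoring".

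Table 6.1 schedules the remote recording three times. The first is "for 2 weeks after BL", the second is "for 2 weeks after V3", and the third follows Visit 4 in the same way. Section 7.5.1, which sits under the Long Term Intervention Period, repeats the second: "At the end of Visit 3, all patients will perform a second remote gait monitoring period".

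Section 7.4.3 gives the order of events at Visit 3. The choice comes first: "Also, the patients further allocation is to be decided (Section 7.4". Then "the patients will return home with their devices (as applicable based on their new or unchanged treatment", and they go on into Remote Gait Monitoring 2. Section 7.5 describes the three options (continue, switch, stop) and keeps stoppers in the study for data collection.

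Section 6.1 says that the equal allocation holds from the Baseline Visit to Visit 3 only, and that data after that point are exploratory.

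**The concern.** The endpoint is labelled Week 12, but every day of the recording that must supply it lies after the point at which patients may leave their randomised treatment. Two uses of the data are affected.

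- **Comparison by randomised arm at Week 12.** Controls who start FeetMe at Visit 3 may contribute a control value recorded during FeetMe use. FeetMe patients who stop or move to conventional physiotherapy may contribute a FeetMe value recorded without it. Section 6.1 expects some of this: it says the design lets controls who find no therapist obtain treatment by switching.
- **Within-patient comparisons.** Section 6.1 also plans to compare the two treatments in patients who switch, and to assess maintenance in those who stop. For remote gait, the Week 12 value that should anchor both is taken after the change of regimen, so the Week 12 to Week 24 change starts from the wrong side of it.

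Section 5.1 presents home monitoring as a special feature of the device and a new source of evidence, so the data should match their label.

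**Working it through.** No figure in the plan is in dispute. The sample size concerns the in-clinic 6-minute walk test (6MWT) and does not enter. The check sets the recording windows against the allocation timeline.

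**1. Windows (Table 6.1; sections 7.4.1, 7.5.1, 7.5.4).**

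| Recording | Starts at | Nominal weeks | Label in the endpoint | Allocation status |
|---|---|---|---|---|
| 1 | Baseline Visit | 0–2 | Baseline | randomised; how much is on treatment is unclear |
| 2 | Visit 3 | 12–14 | Week 12 (Visit 3) | after the choice to continue, switch or stop |
| 3 | Visit 4 | 24–26 | Week 24 (Visit 4) | after the 12-week second period |

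**2. Effect of the visit window.** Visit 3 may fall 7 days either side of week 12. At week 11 the second recording runs over weeks 11–13, and at week 13 over weeks 13–15. It starts from the visit in each case, so none of its 14 days precedes the choice.

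**3. Can another recording stand in?** The Synopsis asks all patients to wear the insoles for 14 days after the Baseline Visit, after which only FeetMe patients go on using them for their programme. The weekly remote 6MWT is done in the FeetMe arm only (section 8.1.2). No remote data are scheduled for controls in the last weeks of the randomised period, so no later analysis rule can recover an end-of-period value for them.

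**4. What is recorded.** In the first window, "All patients will use the insoles remotely while performing their day-to-day activities (including physiotherapy) for two weeks"; section 7.5.1 says the same for the second. For a patient who has just changed regimen, the recording may therefore include sessions of the new one.

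**5. Size, by assumption only.** Let D be the arm contrast at the end of the randomised period. Let f be the sum of the two arms' shares of patients who leave their regimen, and w the average fraction of D by which leavers have moved towards the other arm during the recording. Then

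observed contrast / D = 1 − w × f.

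- f = 0.2, w = 0.25: 1 − 0.05 = 0.95
- f = 0.4, w = 0.5: 1 − 0.20 = 0.80
- f = 0.4, w = 1: 1 − 0.40 = 0.60

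The protocol gives neither f nor w. The last line is an extreme in which leavers cross over completely at once.

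**The case against.** The strongest reply is that the protocol already separates the groups. Table 5.1 sets the exploratory endpoints beside objectives for patients who continue, stop and switch. Section 9.5.3 organises the exploratory analysis along the same lines, with other endpoints described only, and no passage spells out a randomised-arm test of remote gait at Week 12. This stands as far as it goes and removes part of the worry about mixed arms. It does not supply a Week 12 value from before the change, which the switch and maintenance objectives need.

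A reader might infer more than the documents support:

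- **That Week 12 remote gait says nothing about the randomised treatment.** Continuers are still on it in weeks 12–14.
- **That every switcher or stopper is recorded on the wrong regimen.** Controls moving to FeetMe must first be trained, and FeetMe patients moving to conventional physiotherapy must arrange it themselves (section 7.5), so some may not have started within 14 days. Section 6.1 says benefit typically shows after ten weeks, and section 4.1.2 reports gains from some forms of exercise lasting up to six months. A small w is plausible.
- **That a large share, such as a third or half of controls, is affected.** No switch rate is given anywhere.
- **That the Baseline recording is wholly on treatment.** Section 7.4 has the regimen begin after the Baseline Visit. The Synopsis has FeetMe patients move to their programme schedule after the 14 days, and section 4.4 starts the programme with remote training once the devices are at home. The text leaves this open.

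**Conclusion.** The mismatch between label and schedule is in the text and needs no assumption: the remote-gait endpoint has no recording from the end of the randomised period. For switchers and stoppers the Week 12 value may reflect the new regimen. Any comparison by randomised arm is then diluted rather than invalid, and remote gait loses its pre-change reference for the switch and maintenance objectives.

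The dilution depends on how many patients leave and how fast their gait changes, and the protocol states neither. The point is minor. The endpoint is exploratory and summarised descriptively (section 9.2.6). The primary, key secondary and other secondary endpoints do not use these windows, and the 6MWT is done at Visit 3 itself, so in-clinic gait keeps its pre-change reference.

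**What to change.** Schedule the second remote window in the two weeks before Visit 3 (nominal weeks 10–12) and the third in the two weeks before Visit 4 (weeks 22–24), counted back from the booked visit date. Edit Table 6.1, sections 7.4 and 7.5 and the matching Synopsis text. Wear time is unchanged at two weeks per window. The cost is a reminder to patients before each visit.

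One point must be settled first. The Synopsis says every patient is again provided with insoles at Visit 3, while section 7.4.3 has patients bring their devices to that visit. These should be reconciled, with confirmation that control patients keep their insoles until Visit 3.

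Moving these two windows does not change the first, which should be labelled weeks 0–2 after the Baseline Visit.

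If the windows stay where they are, label the second and third weeks 12–14 and 24–26, label the first as above, and present remote gait by post-Visit 3 choice as well as by randomised arm. That costs only text, but it does not restore the missing reference value.

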7.5.2 Visits 1.2 and 2.2

Four and eight weeks after Visit 3, that is at week 16 and week 20 from Baseline Visit patients who decided to switch will take part in a virtual remote visit (Visit 1.2 and Visit 2.2 respectively).

Patients will be asked to fill in the following questionnaires:

- PDSS-2
- Pain VAS
- Parkinson Disease Questionnaire, Short Form (PDQ-8).
- 7.5.3 Visit 4

Twelve weeks after Visit 3, that is, at the end of the 12-week Long Term Intervention Period, all patients will participate in an in-clinic visit (Visit 4), where they will perform the same series of assessments as in the Baseline Visit and Visit 3. Patients will need to bring their FeetMe devices, their diaries, trackers and filled-in questionnaires to the visit.

The following assessments will be performed at Visit 4:

- Gait Assessments, which must be performed in the ON-phase:
 - 6 Minutes Walk Tests (6MWT)
 - Mini-BESTest.

During the 6MWT and the Mini-BESTest, patients must wear the insoles. Specific instructions set out in the Site User Manual must be followed when setting up and executing the assessments.

- Disease specific rating scales:
 - MDS-UPDRS
- Other Assessments:
 - FOG-Q
 - PDSS2
 - Pain VAS
 - PDQ39
 - Clinical Global Impression of Improvement / Patient Global Impression of Improvement (CGI/PGI-I)
- Potential adverse events and change in concomitant medication since the last contact.

- The source documents must be collected from the patients and the diary and tracker transcribed into the database.
- At the end of the visit the patients will return home with their devices and proceed into the Remote Gait Monitoring 3 (Section 7.4.4).

7.5.4 Remote Gait Monitoring 3

At the end of Visit 4, all patients will take the FeetMe Insoles with them to their homes. All patients will again use the insoles remotely while performing their day-to-day activities (including physiotherapy) for two weeks. Data will be recorded in standalone mode.

Once the Remote Gait Monitoring 3 period is completed, all patients will return all the FeetMe devices to the site via courier. The site personnel will make sure the data is downloaded as described in the Site User Manual.

7.6 End of Study Visit

An End of Study Visit will be scheduled remotely. Patients will receive a phone call from the Investigator who will ask them about:

- Potential adverse events and change in concomitant medication since the last contact.
- Satisfaction with the medical device and smartphone applications (Appendix D).

Once the End of Study Visit is completed, the patient's participation in the study will be considered concluded.

7.7 Withdrawal / Early Termination Visit

Patients may withdraw from the study at any time at their request or following a decision of the Investigator or Sponsor. In case of termination due to a patient's decision, every effort should be made to determine the primary reason for withdrawal and to document it in the eCRF.

8 STUDY ASSESSMENTS

8.1 Gait Assessments

8.1.1 6 Minutes Walk Test (6MWT)

The 6 Minutes Walk Test is a standard performance exercise test designed to assess the functional capacity and walking endurance of a patient in the clinical setting (American Thoracic Society, 2002). The 6MWT consists of a single activity, administered by the Investigator, in a flat indoor corridor at least 30 metres in length, marked every three metres and delimited by cones indicating turnaround points. During the 6MWTs the patients should be in ON state. They will be wearing the insoles. The test will be recorded using a FeetMe application.

The Investigator instructs the patient to walk at a comfortable pace and cover the longest distance possible, then measures the total distance the subject can travel over a six minute period. The total score is the walked distance in metres. This test can be administered by the Investigator or by health care personnel trained in the procedures of the evaluation. The 6MWT takes approximately 10 minutes to complete. The date and time of the assessment are to be recorded in the eCRF.

The standard 6MWT will be performed during the on site visits at BL, Visit 3 and Visit 4. Detailed instructions on how to execute the test are given in the Site User Manual.

8.1.2 Remote 6 Minutes Walk Test (6MWT)

The remote version of the 6MWT is a self-administered adaptation of the 6MWT (see paragraph 8.1.1), designed to assess the functional capacity and walking endurance of a patient in a more familiar setting (e.g. home, workplace). This test consists of a single activity, self-administered by the subject in a place of their choosing, preferably featuring a hard, flat surface which presents sufficient space for an adult person to walk safely, without objects or obstacles hindering the subject's performance or putting the subject in danger of falling or hurting themselves. The remote 6MWT shall be performed outdoors to avoid many U-turns. The patient is asked to do the test in ON conditions and at the same time and place every week.

Weekly 6MWT tests are part of the FeetMe rehabilitation program, therefore only patients who are on the FeetMe arm will perform them using the FeetMe Rehabilitation application. The application instructs the patient to walk at pace to cover the longest distance possible, then measures the total distance the subject can travel over a six minute period. The total score is the walked distance in metres. The remote 6MWT takes approximately 10 minutes to complete. The date and time of the assessment will need to be recorded in the eCRF.

8.1.3 Mini Balance Evaluation Systems Test (Mini-BESTest (Appendix L))

The Mini Balance Evaluation Systems Test is a standard performance rating scale designed to evaluate a patient's static and dynamic balance (Franchignoni et al., 2010). The assessment, administered by the Investigator, includes fourteen balance-related tasks, each scored on a scale from 0-2 based on the observed patient ability and independence in performing each exercise. The Investigator evaluates the patient's performance and assigns a score to each exercise. The individual scores are subsequently summed to yield a total score ranging from 0 to 28, where higher scores indicate better performance. The Mini-BESTest takes approximately 15 minutes to complete. During the test the patients should be in ON state and will be wearing the insoles. The date and time of the assessment and the sub-scores will be captured in the eCRF.

The MiniBESTest will be performed during the on site visits at BL, Visit 3 and Visit 4. Detailed instructions on how to execute the test are given in the Site User Manual.

8.2 Medical History

A complete past medical history will be collected by the Investigator or appropriate site staff according to standard practice and recorded in the eCRF. This will include a history of all previous diseases and illnesses, those currently being treated until the time of the screening visit, as well as those which have any residual effects on the patient's health. Moreover, surgical history will be collected, including all invasive procedures the patient has undergone until the time of the screening visit. Previous falls should be recorded to the extent possible.

8.3 **Prior- and Concomitant Medication**

Details of all medication taken \leq 3 months prior to the Screening Visit or during the study until the EOS Visit will be collected by the Investigator or the site staff according to standard practice and recorded in the eCRF.

Patients are eligible if on stable treatment of PD medication for at least 30 days before screening. Major changes in PD treatment during the first 3 months of the study are not allowed. What is considered a major change is up to investigator judgement, nevertheless, in principle anything that would alter the gait of the patient is considered as such. For example, adaptation of the levodopa dose to maintain current level of ambulation is not considered a major change, while changing the posology of the

treatment (e.g.: switching from per os to parenteral), or introducing a new one would classify as one. Ideally no major changes should be issued during the whole duration of the study in other medication that can influence overall data interpretation either (e.g.: antidepressants).

In case major changes in concomitant medication are unuvoidable, either due to the worsening of a disease or a new disorder, it must be recorded in the eCRF specifying the reason (e.g.: worsening of a medical history, adverse event or as a new adverse event) and will be taken into account during analysis.

